	supported by several well-designed and conducted clinical studies			
	and it has showed a good benefit risk profile, unchanged in nature			
	and frequency over more than 30 years of clinical paediatric use.			
	A recent meta-analysis by Schaad et al. 2010 ² of 8 double-blind			
	placebo-controlled trials conducted in children aged 1-12 years			
	affected by recurrent infective episodes (\geq 3 RTIs in 6 months) has			
	shown that the administration of OM-85 significantly reduced the			
	mean number of RTIs by 35% vs placebo and that a lower			
	proportion of treated patients (26.2%) experienced RRTIs. This			
	effect was more evident in patients with the highest number of			
	infectious in the year prior to study $entry^2$.			
	The majority of studies used a children posology of 1 daily dose			
	(3.5mg) for 10 days repeated for 3 consecutive months followed by			
	3 months or 9 months follow-up. In one study 2 cycles (10 days/3			
	months) at a 6-months intervals were used.			
	An effective and well tolerated prevention of RRTIs with OM-85			
	could result not only in a positive effect on children's quality of life			
	courd result not only in a positive cricer on children's quanty of file			

	but also in economic benefit for patients' families and societies as		
	recently reported in a pharmacoeconomic study by Zaniolo et al.		
	2013^3 and Ravasio et al. 2015^4 .		
	Because OM-85 significantly reduces RTIs in children, it is		
	expected to be able to reduce the adenoid tissue size as a		
	consequence of fewer inflammatory RTIs.		
	References:		
	1. De Benedetto F, at al. Prevention of respiratory tract infections		
	with bacterial lysate OM-85 Broncho-munal in children and		
	adults: a state of the art. Multidiscip Respir Med. 2013 May		
	22;8(1):33		
	2. Schaad UB. OM-85 BV, an immunostimulant in pediatric		
	recurrent respiratory tract infections: a systematic review.		
	World J Pediatr 2010; 6(1): 5-12.		
	3. Zaniolo O et al. Costo/efficacia della prevenzione di infezioni		
	alle prime vie aeree mediante un estratto batterico		
	immunostimolante aspecifico (OM-85). Farmaeconomia e		
	percorsi terapeutici 2013; 3(6):169-184		
	4. Ravasio R. Economic analysis of the immunostimulant OM-85		
	for the prevention of paediatric recurrent upper respiratory tract		
	infections. Global & Regional Health Technology Assessment		
	2015; 0(0): 00-00. DOI: 10.5301/GRHTA.5000200.		
Objectives			
J	Primary Objective:		

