	• Reduction of number of RTIs within 12 months		
	Secondary Objective(s):		
	Reduction in duration of RTIs		
	Reduction of antibiotic use		
	• Reduction of absenteeism (missed school days or missed days of		
	work for parents)		
	Adenoid and tonsil health survey		

 Reduction of the size of adenoid tissue (described in appendix 3) Reduction of surgery need Design, incl. This is a randomised, double-blind, placebo-controlled, parallel group, phase IV study. First group will receive OM-85 (10-10-10 standard treatment regimen) Second group will receive matching placebo at the same posology (10-10-10). A second cure of treatment will be given 6 months after inclusion. Patients will be recruited from 01 September 2017 to 01 March 2018. The trial will begin in September 2017 and will be completed in March 2019. By this way every patient will be studied over all seasons (1 year study). Children (age: 2-6 years) Who experienced recurrent RTIs (at least 3 episodes in 6 months before the inclusion) Who have symptoms of AH (snoring; mouth breathing awake; mouth breathing asleep; nasal congestion; hyponasal voice; chronic nasal discharge; daytime drowsiness, or hyperactivity; restless sleep; sleep apnoca <15 sec; night cough; and poor oral intak/weight loss) based on the symptoms score questionnaire (described in appendix 1). Exclusion Criteria A Atopy Gastroesophageal reflux Immune deficiency Asthma or allergic rhinitis 		-					

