	gamma globulins, or anticonvulsive drugs within the				
	previous 6 months.				
Endpoints	Primary Endpoint: Cumulative number of RTIs over the 12				
	months.				
	monuis.				
	Secondary Endpoints:				
	• Duration in days of RTIs				
	• Antibiotic use (n. of cycles and days)				
	Missed school/work days				
	• Adenoid and tonsil survey (described in appendix 1 of the				
	original protocol)				
	• Size of adenoid tissue over the 12 months according to				
	radiographic and flexible nasopharyngoscopic evaluation (described				
	in appendix 3 of original protocol).				
	Surgery need				
	• AEs				
	Patients will be recruited from 01 September 2017 to 01 March				
Procedures	2018. The trial will begin in 01 September 2017 and will be				
	completed 01 March 2019.				
	Children with the ages of 2-6 years who have recurrent RTIs and				
	AH will be evaluated for the eligibility for the study. When eligible				
	for the study, children's all demographic characteristics will be				
	recorded (Table 1). Eligible children will be evaluated by ear-nose-				
	throat (ENT) specialist and flexible laryngoscopy and radiographic				
	evaluation of adenoid size will be performed in order to measure the				
	adenoid size. All children will be evaluated by an allergy specialist.				
	Complete blood count, serum IgG, IgA, IgE, IgM will be measured.				

Skin prick test will be performed with common allergens.

All children will be randomized into two study arms (active treatment and placebo). OM-85 3.5 mg capsule or placebo will be given according to the standard treatment schedule (10-10-10) for the three consecutive months. All patients will receive 2 cures of treatment at the beginning and 6 Months after inclusion in the study. Every patients will be followed-up for 12 months.

Patients (and care giver/parents) will be given a symptom score form (Table 2) in order to record all nasal symptoms, signs and duration of RTIs, antibiotic use, days of absenteeism from school and from work for family members, monthly.

All patients will be asked to come to the clinic when they have symptoms of RTI in order to diagnose the type of RTIs. Then they will be asked to complete the infection form during the acute RTIs (Table 3).

Every 3 months they will fill in the Tonsil and Adenoid Health Status Survey (Table 4).

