Appendix 1. Study Forms

Table 1. Demographic charecteristics

PATIENT FOLLOW-UP FORM		
Date		
Patient Number		
Treatment group (Randomisation code)		
Name Surname		
Birth date		
Gender		
Smoking at home		
Family history of asthma		
Family history of atopy		
DPT		
lgG		
IgA		
lgE		
IgM		
FIRST VISIT		
RTIs in previous 12 months		
RTIs in previous 6 months		
Number of hospitalisation in previous 12 months		
Total days of hospitalisation in previous 12 months		
Total days of absenteisim from school		
Total days of absenteisim from work for mother		
Total days of absenteisim from work for father		
Antibiotic use in previous 12 months		
Number of box		
Total number of days		
Symptome score		

QoLQ (Score)	
Adenoid size	
Radiological (AC/SP ratio)	
Nasopharingoscope (perceived percent obstruction of the choana)	

Table 2. Symptomes score (will be completed for each month)

Symptomes	none (0 point)	rarely (1 point)	frequently (2 points),	constantly (3 points)
Snoring				
mouth breathing awake				
mouth breathing asleep				
nasal congestion				
hyponasal voice				
chronic nasal discharge				
daytime drowsiness, or hyperactivitiy				
restless sleep				
sleep apnea <15 sec				
night cough				
poor oral intake/weight loss				

Scores from eleven symptoms were added together to provide a total symptom score of 33.

Table 3. Infection form (will be completed for each infection)

Type of RTI	
Duration of RTI	
Antibiotic consumption (days)	
Days of absenteism from school	
Days of absenteism from work for family members	

Table 4. Tonsil and Adenoid Health Status Survey (It will be completed by the parents in every
3 months)

TONSIL AND ADENOID SURVEY

We are conducting a study on children with tonsil or adenoid problems, and we are interested in the type of health problems that your child is having related to his (her) tonsils and adenoids. There are no correct or incorrect answers, and your opinion is most important to us. The survey is completely voluntary and will take about 3 minutes to complete.

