Statistical method:

All analyses will be performed with a commercially available software program (SPSS Statistical Software, version 11.5; SPSS, Inc, Chicago, Ill). The Shapiro-Wilks test will be used to evaluate normality of the distributions collected. When variables were normally distributed, they were expressed as means (SDs); otherwise, they will be expressed as medians and interquartile ranges (25th-75th percentiles). The χ^2 test will be used for categorical variables and expressed as observation counts (in percentages). An ANOVA (or Mann-Whitney U depending on the normality of data) statistics will be used to compare means between both treatment groups for continuous variables. Bonferroni multiple comparison test will be used to compare paired intervals (0-3, 0-6 months). All P values are 2-tailed; a P value of less than .05 are considered statistically significant.

Sample Size:

In one study OM-85 group showed 3 less RTIs compared with placebo over 12 months period. A sample size of 54 randomized patients (27 per group) will provide at least 80% power to detect a mean difference of at least 2.0 RTIs between the two groups assuming a SD of 2.55 and assuming a drop-rate of 20% after 6 months, total of 68 patients (34 per group) will be recruited to the study.¹

Reference:

María Dolores Gutiérrez-Tarango and Arturo Berber. Safety and Efficacy of Two Courses of OM-85 BV in the Prevention of Respiratory Tract Infections in Children During 12 Months. CHEST 2001; 119:1742–1748

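### The primary comparison of 12-month RTI counts ignores the prior-12-month RTI count already on the baseline form; a pre-specified covariate would add precision at almost no cost

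*Protocol*

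**What the plan says.** - **Endpoint.** The Protocol (Endpoints) makes the primary endpoint "Cumulative number of RTIs over the 12" months.
- **Test.** The SAP (Statistical method) names ANOVA, or Mann-Whitney U depending on normality; these "statistics will be used to compare means between both treatment groups for continuous variables". The Protocol (Statistical Methods) says the same. Neither names a covariate or stratum for the primary comparison.
- **Baseline data.** Protocol Appendix 1, Table 1 records both "RTIs in previous 12 months" and "RTIs in previous 6 months" at the first visit.
- **Entry.** Children qualify on "at least 3 episodes in 6 months before the inclusion" (Inclusion Criteria). "Patients will be recruited from 01 September 2017 to 01 March 2018" (Design). Follow-up lasts one year, so that each child's outcome window covers every season.
- **Randomisation.** The ratio is 1:1, with 34 per arm. No stratification is stated.
- **Rationale.** The Protocol cites a meta-analysis in which the OM-85 "effect was more evident in patients with the highest number of" infections in the year before entry.

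**The concern.** Children admitted because of recurrent infections are likely to differ in how often they fall ill, and the count over the past year is the natural measure of that. The trial collects it and the Rationale treats it as important, yet the primary test leaves it out. Two things follow in a trial of 68. Outcome variation that baseline could explain stays in the error term, and chance imbalance in baseline infection rate is not corrected. If imbalance is noticed after unblinding, any adjustment then becomes a post hoc choice.

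Which baseline count to use also matters. A 1 September entrant qualifies on March to August infections and a 1 March entrant on September to February infections. The 6-month count therefore does not measure the same thing in every child, whereas the 12-month count spans a full year for all.

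**Working it through.** **1. The plan's own figure.** Inputs from the SAP (Sample Size): difference 2.0, SD 2.55, two-sided 5%, 80% power, 20% dropout.

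- Normal approximation: n = 2(1.96 + 0.842)² × 2.55² / 2.0² = 25.5, so 26 per arm.
- By the t distribution, 26 per arm gives 79.2% power. With 27, the noncentrality is 2.0 / (2.55 × √(2/27)) = 2.88 on 52 df, giving 80.7%.
- Dropout: 27 / 0.8 = 33.75, so 34 per arm and 68 in all.

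The stated sample size reproduces.

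**2. Power with the covariate.** With correlation ρ between baseline and outcome counts, the residual SD is 2.55 × √(1 − ρ²), on 51 df. The documents give no ρ, so a range is assumed.

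| ρ | Residual SD | Power, 27 per arm | n per arm for 80% |
|---|---|---|---|
| 0 | 2.55 | 80.7% | 27 |
| 0.2 | 2.50 | 82.3% | 26 |
| 0.3 | 2.43 | 84.2% | 25 |
| 0.4 | 2.34 | 87.0% | 23 |
| 0.5 | 2.21 | 90.4% | 21 |

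**3. Chance imbalance.** At 27 per arm, the 95% range of baseline imbalance is ±1.96 × √(2/27) = ±0.53 SD. It shifts the unadjusted difference by up to 0.53 × ρ × 2.55: about 0.3 RTIs at ρ = 0.2 and 0.7 at ρ = 0.5.

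**4. Plausible ρ, and which count to use.** Assumed model: each child's annual rate is gamma distributed, counts are Poisson and recorded without error, half the children enter at each end of recruitment, and the cold-to-warm half-year ratio is 1.5 to 3. Results are for eligible children.

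| Mean, CV of annual rate | Outcome SD | ρ, 12-month count | ρ, 6-month count | September minus March entrants (RTIs per year) |
|---|---|---|---|---|
| 5, 0.2 | 2.5 | 0.14–0.15 | 0.06–0.08 | 0.1–0.25 |
| 4, 0.3 | 2.5 | 0.22–0.24 | 0.10–0.13 | 0.15–0.4 |
| 5, 0.6 | 4.1–4.3 | 0.56–0.59 | 0.27–0.40 | 0.7–1.7 |

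Only the first two rows agree with the planned SD. There ρ is about 0.15 to 0.25, and adjustment adds 1 to 2 points. The 12-month count predicts better in every row. With no seasonality at all it still leads (0.22 against 0.14 at mean 4, CV 0.3), because it covers more time; seasonality widens the gap.

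**5. If children vary more than planned.** By the same formula, at SD 3.2 and ρ = 0.4 power goes from 62% to 69%. At SD 4.15 and ρ = 0.57 it goes from 41% to 56%.

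**6. Validity.** With an added 0, 1 or 2 RTI shift between early and late entrants, the simulated type I error of the unadjusted t-test was 4.9% to 5.2%.

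**The case against.** The strongest reply is that nothing is broken. Allocation is randomised and blinded, the unadjusted test holds its level, chance imbalance is already reflected in the standard error, and the sample size reproduces. At the planned SD the likely gain is only 1 to 2 points. All of that stands, and it makes this a matter of efficiency rather than error.

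Three stronger readings are tempting, and the documents do not support them.

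- **That the entry rule makes September entrants so much more infection-prone that it threatens the result.** The documents give no seasonal RTI rates, so even the direction is an assumption. Gaps above 1 RTI arise in models whose outcome SD exceeds 4, where unadjusted power would be 39% to 42%; they cannot be paired with power figures at SD 2.55. Nor should a gap between entrants be set against the 2.0 target between arms. The chance difference between arms in the share of early entrants has SD √(0.25 × 2/34) = 0.12, so a 0.4 RTI gap moves the arm contrast by about 0.05, and a 1.7 gap by about 0.2.
- **That the comparison is biased.** Entry date is independent of arm under randomisation.
- **That the Rationale's remark about children with most prior infections calls for this covariate.** It describes a treatment effect that varies with baseline, which a main-effect covariate does not address. It shows only that the plan regards the prior-year count as relevant.

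**Conclusion.** The point holds as a missed gain in precision on the primary endpoint. The unadjusted comparison is valid, but it sets aside a baseline measure already on the form, in a design with 0.7 points of power to spare. At the planned SD of 2.55 the probable gain is 1 to 2 points. It would reach 84% to 90% power only if the correlation were 0.3 to 0.5, which is higher than models matching that SD suggest. The benefit is greatest where the trial is most exposed, when children vary more than planned.

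These sizes rest on assumed correlations and a normal-theory ANCOVA. Error in recording the prior-year count would lower the correlation and the gain. The entry-date gap is about 0.1 to 0.4 RTIs at the planned SD if RTIs are seasonal. It matters here only as a further reason to prefer the 12-month count.

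**What to change.** Add one sentence to the SAP (Statistical method), mirrored in the Protocol, naming a single primary model before unblinding. Either of these would do:

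- ANCOVA of the 12-month RTI count on arm, with the Table 1 prior-12-month RTI count as covariate; or
- a negative binomial model of the same count on arm with the same covariate.

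Choose one now, and do not let a normality test decide between models once data are in. Use the 12-month count, not the 6-month one. The unadjusted comparison can stay as a sensitivity analysis.

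The cost is a short SAP amendment. The variable is already collected, so no visit, form, eligibility criterion or sample size changes. If the negative binomial model is chosen, confirm that the named software version can fit it.

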awake; mouth breathing asleep; nasal congestion; hyponasal voice; chronic nasal discharge; daytime drowsiness, or hyperactivity; restless sleep; sleep apnoea <15 sec; night cough; and poor oral intake/weight loss) based on the symptoms score questionnaire (described in appendix 1). Exclusion Criteria • Atopy • Gastroesophageal reflux • Immune deficiency • Asthma or allergic rhinitis		months before the inclusion)					
voice; chronic nasal discharge; daytime drowsiness, or hyperactivity; restless sleep; sleep apnoea <15 sec; night cough; and poor oral intake/weight loss) based on the symptoms score questionnaire (described in appendix 1). • Atopy • Gastroesophageal reflux • Immune deficiency • Asthma or allergic rhinitis		• Who have symptoms of AH (snoring; mouth breathing					
hyperactivity; restless sleep; sleep apnoea <15 sec; night cough; and poor oral intake/weight loss) based on the symptoms score questionnaire (described in appendix 1). • Atopy • Gastroesophageal reflux • Immune deficiency • Asthma or allergic rhinitis		awake; mouth breathing asleep; nasal congestion; hyponasal					
Exclusion Criteria • Atopy • Gastroesophageal reflux • Immune deficiency • Asthma or allergic rhinitis		voice; chronic nasal discharge; daytime drowsiness, or					
symptoms score questionnaire (described in appendix 1). • Atopy • Gastroesophageal reflux • Immune deficiency • Asthma or allergic rhinitis		hyperactivity; restless sleep; sleep apnoea <15 sec; night					
Exclusion Criteria • Atopy • Gastroesophageal reflux • Immune deficiency • Asthma or allergic rhinitis		cough; and poor oral intake/weight loss) based on the					
 Exclusion Criteria Gastroesophageal reflux Immune deficiency Asthma or allergic rhinitis 		symptoms score questionnaire (described in appendix 1).					
 Gastroesophageal reflux Immune deficiency Asthma or allergic rhinitis 		• Atopy					
Asthma or allergic rhinitis	Exclusion Criteria	Gastroesophageal reflux					
		Immune deficiency					
		Asthma or allergic rhinitis					
Premature delivery		Premature delivery					
Anatomic alterations of the respiratory tract; chronic		• Anatomic alterations of the respiratory tract; chronic					
respiratory		respiratory					

	diseases (tuberculosis and cystic fibrosis); autoimmune				
	disease; liver				
	Kidney failure; malnutrition; cancer				
	Treatment with inhaled or systemic corticosteroids within				
	the previous month				
	• Treatment with immunosuppressants, immunostimulants,				
	gamma globulins, or anticonvulsive drugs within the				
	previous 6 months.				
Endpoints	Primary Endpoint: Cumulative number of RTIs over the 12				
	months.				
	monuis.				
	Secondary Endpoints:				
	• Duration in days of RTIs				
	• Antibiotic use (n. of cycles and days)				
	Missed school/work days				
	• Adenoid and tonsil survey (described in appendix 1 of the				
	original protocol)				
	• Size of adenoid tissue over the 12 months according to				
	radiographic and flexible nasopharyngoscopic evaluation (described				
	in appendix 3 of original protocol).				
	Surgery need				
	• AEs				
	Patients will be recruited from 01 September 2017 to 01 March				
Procedures	2018. The trial will begin in 01 September 2017 and will be				
	completed 01 March 2019.				
	Children with the ages of 2-6 years who have recurrent RTIs and				
	AH will be evaluated for the eligibility for the study. When eligible				
	for the study, children's all demographic characteristics will be				
	recorded (Table 1). Eligible children will be evaluated by ear-nose-				
	throat (ENT) specialist and flexible laryngoscopy and radiographic				
	evaluation of adenoid size will be performed in order to measure the				
	adenoid size. All children will be evaluated by an allergy specialist.				
	Complete blood count, serum IgG, IgA, IgE, IgM will be measured.				

Skin prick test will be performed with common allergens.

All children will be randomized into two study arms (active treatment and placebo). OM-85 3.5 mg capsule or placebo will be given according to the standard treatment schedule (10-10-10) for the three consecutive months. All patients will receive 2 cures of treatment at the beginning and 6 Months after inclusion in the study. Every patients will be followed-up for 12 months.

Patients (and care giver/parents) will be given a symptom score form (Table 2) in order to record all nasal symptoms, signs and duration of RTIs, antibiotic use, days of absenteeism from school and from work for family members, monthly.

All patients will be asked to come to the clinic when they have symptoms of RTI in order to diagnose the type of RTIs. Then they will be asked to complete the infection form during the acute RTIs (Table 3).

Every 3 months they will fill in the Tonsil and Adenoid Health Status Survey (Table 4).

Every 3 months patients will be asked to come to the clinic and all their records will be collected and they will be evaluated by the ENT specialist for the adenoid tissue size. All these parameters will be recorded in specific forms by the investigator (Table 5).

Patients will be allowed to use nasal corticosteroids, antihistaminic drugs and flu vaccine during the study period and all these study medications will be recorded.

At the end of the study (12 months), immunoglobulin levels will be measured to compare them with basal level.

	1				
Sample Size	A total of 68 patients will be randomized in the study in a 1:1 ratio				
	to Active or Placebo groups.				
	Active group: 34 patients				
	Placebo group: 34 patients				
N ^o Sites					
	Number of study centers: 1				
	Study center: [name] Maternity and Children Research and				
	Training Hospital, Department of Pediatric Allergy and				
	Immunology, Ankara, TURKEY.				
	Study Coordinator and Principal Investigator:				
	[name] M.D. Associate Prof. of Pediatrics and Pediatric				
	Allergy, Training staff on Pediatric Allergy				
	Other Investigators:				
	[name] M.D. Professor of Pediatrics & Subspecialist on				
	Pediatric Allergy and Pediatric Pulmonology				
	Chief of Pediatric Allergy and Immunology Department				
	[name] M.D. Otolaryngologist				
	[name] M.D. Radiologist				
	Statistical method:				
Statistical Methods	All analyses will performed with a commercially available software				
	program (SPSS Statistical Software, version 11.5; SPSS, Inc,				
	Chicago,Ill).				
	The Shapiro-Wilks test will use to evaluate normality of the				
	distributions collected. When variables were normally distributed,				
	they were expressed as means (SDs); otherwise, they will express as				
	medians and interquartile ranges (25th-75th percentiles). The x^2 test				
	will use for categorical variables and expressed as observation				
	counts (in percentages). An ANOVA (or Mann-Whitney U				
	depending on the normality of data) statistics will be used to				
	compare means between both treatment groups for continuous				
	variables. Bonferroni multiple comparison test will use to compared				
	paired intervals (0-3, 0-6 months). All P values are 2-tailed; a P				
	pared intervals (0.5, 0.0 inontins). An 1 values are 2-tailed, a 1				

	value of loss than 05 are considered statistically significant					
	value of less than .05 are considered statistically significant.					
	Sample Size:					
	In one study OM-85 group showed 3 less RTIs compared with					
	placebo over 12 months period. A sample size of 54 randomized					
	patients (27 per group) will provide at least 80% power to detect a					
	mean difference of at least 2.0 RTIs between the two groups					
	assuming a SD of 2.55 and assuming a drop-rate of 20% after 6					
	months, total of 68 patients (34 per group) will recruit to the study. ¹					
	Reference:					
	1. María Dolores Gutiérrez-Tarango and Arturo Berber. Safety and Efficacy of Two Courses of OM-85 BV in the Prevention of Respiratory Tract Infections in Children During 12 Months.					
	CHEST 2001; 119:1742–1748					
Planned Timelines	Planned date first patient consented/enrolled/observed: 01					
	September 2017					
	Planned date last patient consented/ enrolled/ observed: 01 March					
	2018					
	Planned date last patient last observation/ treatment: 01 March 2019					
	Planned date CSR (Clinical study report) available: June 2019					

1. Visit	2. Visit	3. Visit	4. Visit	5. Visit	6. Visit
Randomitaz ion of the patients	After randomization treatment plan (OM-85 capsules or placebo given in the first 10 days of each month for 3 months)	Control at the end of 3rd month of treatment (20 days after the last medicine/drug or placebo)	Control after 3 months of last drug or placebo intake and Given the product by the previous randomization again for 3 months	At the end of the second 3-month treatment (20 days after the last drug)	Control after 3 months of the last drug or placebo intake (20 days after the last medicine/drug or placebo)

• Patients will be assessed for type of respiratory infection and additional treatment by researchers (pediatric allergy specialists and/or ENT specialists) in the Pediatric Allergy and Immunology outpatient clinic when symptoms of respiratory tract infection is present.

- Parents will be asked to fill in the relevant form [Symptom Score Form] during this acute respiratory tract infection.
- Every 3 months, parents will be filled.QoLQ "Tonsil and Adenoid Health Status Survey".

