STUDY PROTOCOL

Effect of Vaxoral[®] (OM-85) on frequency of upper respiratory tract infections and size of adenoid tissue in preschool children with adenoid hypertrophy

Study Product(s)	Vaxoral [®] (OM-85)			
Indication	Recurrent RTIs, adenoid hypertrophy			
Sponsor	[name] Maternity and Children Research and Training			
	Hospital, Department of Pediatric Allergy and Immunology,			
	Ankara, TURKEY			
Anticipated	Taulasa			
Countries	Turkey			
Introduction	OM-85 significantly reduces RTIs in children. This effect was			
	proved by many clinical studies and meta-analyses ¹ . A Cochrane			
	meta-analysis first published in 2006 and updated recently (Del-			
	Rio-Navarro 2012) showed that immunostimulants (IS) could			
	reduce acute RTIs (ARTIs) by almost 39% when compared to			
	placebo. Among the different IS, OM-85 showed the most robust			
	evidence with 4 trials of "A quality" according to the Cochrane			
	grading criteria. Pooling six OM-85 studies, the Cochrane review			
	reported a mean number of ARTIs reduction by -1.20 [95% CI: -			
	1.75, -0.66] and a percentage difference in ARTIs by -35.9% [95%			
	CI: -49.46 , -22.35] compared to placebo ¹ .			
	Adenoid hypertrophy (AH) is one of the most important respiratory			
	disease in preschool children ² . In normal conditions adenoid tissue			
	enlarges up to 5 years and become smaller afterwards. But in some			
	children who have recurrent URTIs, it keeps growing and this can			
	be associated with complications ² . AH may cause recurrent			
	respiratory infections and each infection contributes to enlargement			
	of adenoid tissue thus promoting a vicious cycle. Additionally			
	enlarged adenoids are known to be reservoir for microbes and cause			
	of recurrent or long lasting RTIs ³ .			
	AH is associated with chronic cough, recurrent and chronic			

sinusitis, recurrent tonsillitis, recurrent otitis media with effusion, recurrent other respiratory problems such as, nasal obstruction and sleep disturbances, sleep apneas²⁻³. Eventually, AH causes loss of appetite and growth delay; it is often associated with misuse or over use of antibiotics and often eventually requires surgery. It decreases quality of life both in children and parents and it represents a burden not only for families but also for HCS and society due to increased health cost⁴.

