Appendix 3. Radiographic evaluation of adenoid size:

Radiographic evaluation of adenoid size by the method of Cohen and Konak (1). Thickness (mm) of "Airway column" (A) and "Soft palate" (B) is measured and A/B ratio is calculated in order to evaluate nasopharyngial airway patency.

Lateral neck radiographs will taken and interpreted by the method of Cohen and Konak by a blinded radiologis (1). According to this method, the thickness of the soft palate (SP) in its superior anterior part and the airway column (AC) immediately posterior to it will measured and AC/SP ratio

was calculated. The measurement will done about 1 cm below the upper end of the soft palate in children > 3 years of age and half a centimetre in younger children. A radiographic example of this method is demonstrated in Figure 1.

Degree of obstruction was graded as follows: AC/SP ≥1 (grade 0 or no obstruction), AC/SP= 0.50-0.99 (grade 1 or mild obstruction), AC/SP= 0.01-0.49 (grade 2 or severe obstruction), AC/SP= 0 (grade 3 or total obstruction).

Flexible nasopharyngoscope:

Topical anesthesia will use in the form of a mixture of lidocaine/ neosynephrine spray that will applied by pressurized nozzle prior to endoscopic examination. The patient will be seated upright in the examination chair without restraint during the exam. A standard 4.0 mm flexible nasopharyngoscope with attached fiberoptic light will be used to perform the nasopharyngoscopy. The data will be recorded as a perceived percent obstruction of the choana by the adenoid pad, as seen through the endoscope.

Lertsburapa K, SchroederJW, Sullivan c. Assessment of adenoid size: A comparison of lateral radiographic measurements, radiologist assessment, and nasal endoscopyInternational Journal of Pediatric Otorhinolaryngology 74 (2010) 1281–1285

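### The plan has no rule for adenoid size measured after adenoidectomy; if values are used as measured, the arm with more surgery looks better

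*Protocol*

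**What the plan says.** The protocol's Endpoints section lists two separate secondary endpoints that bear on each other: "Size of adenoid tissue over the 12 months according to" radiography and flexible nasopharyngoscopy, and surgery need. The second is named but not defined. The Introduction says that adenoid hypertrophy "often eventually requires surgery", without a rate or a time frame, and its research question asks about both adenoid size and the need for surgery.

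Under Procedures, "Every patients will be followed-up for 12 months", and at each 3-monthly visit "they will be evaluated by the ENT specialist for the adenoid tissue size". Neither statement makes an exception for a child who has been operated on.

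Appendix 3 defines the two measures. The endoscopic one is the "perceived percent obstruction of the choana by the adenoid pad". The radiographic one is the AC/SP ratio, whose best category, a ratio of 1 or more, is "grade 0 or no obstruction".

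On analysis, the SAP (Statistical method) says that ANOVA or Mann-Whitney U "statistics will be used to compare means between both treatment groups for continuous variables". The protocol's Statistical Methods section agrees. Neither document has a rule for surgery, a missing-data rule or a defined analysis set. The follow-up form (Appendix 1, Table 5) has fields for adenoid size and hospitalisation but none for an operation or its date.

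**The concern.** Removing the adenoid pad should bring endoscopic obstruction close to 0% and raise the AC/SP ratio. This is inferred from how the measures are defined; the documents do not state it. A child whose disease led to surgery would then enter the size comparison as a large improvement.

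The trial's hypothesis is that OM-85 reduces both adenoid size and the need for surgery. If it does reduce operations, more placebo children have post-operative values, and the size comparison shifts towards placebo. Leaving operated children out does not cure this, because it removes the largest adenoids, mostly from the arm with more surgery. Neither obvious default measures the drug's effect on adenoid size when surgery rates differ between the arms.

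**Working it through.** **The plan's own figure.** The only sample-size figure concerns the primary endpoint (RTI count). With a difference of 2.0 and SD 2.55, the normal approximation gives 2 × (1.96 + 0.84)² × 2.55² / 2.0² = 25.5, so 26 per group. The t-test version gives 26.5, so 27, as stated. Then 54 / 0.8 = 67.5, so 68. The figure reproduces and this point does not affect it.

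**Inputs for adenoid size.** The documents give no surgery rate, SD, expected effect or post-operative value, so all of these are assumptions: 12-month obstruction 65% on placebo, SD 20, true OM-85 benefit 10 points, post-operative obstruction 10%, and larger adenoids operated on more often.

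**Formula.** Let p be the proportion operated on in an arm and R the mean obstruction that surgery removes in those children. With values used as measured:

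observed benefit = true benefit − (p_placebo × R_placebo − p_OM-85 × R_OM-85)

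In simulation with no true effect, placebo looked 5.6 points better at 10% versus 2% surgery and 10.4 points better at 20% versus 5%. Dividing by the rate differences gives 5.6 / 0.08 = 70 and 10.4 / 0.15 = 69, so R is about 70 on placebo. With a true benefit of 10 points it is about 60 on OM-85.

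**Results, true benefit 10 points, 34 per arm.** Three rows use a 36% relative reduction in surgery. That borrows the roughly 36% reduction in infections quoted in the Introduction and is itself an assumption.

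| Surgery, placebo vs OM-85 | Expected operations | Formula | Simulated benefit |
|---|---|---|---|
| 10% vs 10% | 3.4 vs 3.4 | 10 − (7.0 − 6.0) = 9.0 | 8.9 |
| 5% vs 3.2% | 1.7 vs 1.1 | 10 − (3.5 − 1.9) = 8.4 | 8.1 |
| 10% vs 6.4% | 3.4 vs 2.2 | 10 − (7.0 − 3.8) = 6.8 | 6.8 |
| 10% vs 2% | 3.4 vs 0.7 | 10 − (7.0 − 1.2) = 4.2 | 4.0 to 4.1 |
| 20% vs 12.8% | 6.8 vs 4.4 | 10 − (14.0 − 7.7) = 3.7 | 4.1 |
| 20% vs 5% | 6.8 vs 1.7 | 10 − (14.0 − 3.0) = −1.0 | −0.8 |

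With no true effect and equal surgery rates, the mean bias is about 0.1 point.

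**Excluding operated children** leaves about 8.5 of the 10 points at 10% versus 2%, and 7.1 to 7.5 at 20% versus 5%.

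**Power.** With no surgery at all, Mann-Whitney power for 10 points is about 51% at 34 per arm and 42% at 27 per arm. At 10% versus 2% and 34 per arm it falls to 17 to 19%. Rejection rates depend on how surgery is linked to size in the model, so the shifts in means are the firmer result.

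**Worst rank.** A separate run used 27 per arm, mean 60%, SD 20, post-operative 5% and a true benefit of 10 points. At 15% placebo versus 5% OM-85 surgery, the test was significant in 12% of trials with values as measured and in 42% with operated children ranked worst. At 10% in both arms, the figures were 36% and 31%.

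**The case against.** The strongest objection is that the documents never say post-operative values will be used. They are silent. Operated children might be excluded, censored or counted within the 20% dropout allowance, and exclusion gives a smaller bias. This stands, so the point must be put conditionally. It does not remove the point, because following the written schedule and test brings those values in and no sentence keeps them out.

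Second, surgery need is undefined. It may mean an indication or referral, with the operation after follow-up ends, in which case few or no post-operative values would exist. This also stands and is a reason to define the endpoint.

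Third, a reader might infer that a true effect is likely to be hidden or reversed. The documents do not support that. Among the scenarios shown, a reversal appears only at 20% versus 5%, a 75% relative reduction in surgery. With a 36% reduction, about 8, 7 or 4 of the 10 points remain.

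Fourth, carrying forward the last pre-operative value may look like the natural main analysis. It is not neutral. The Introduction says adenoids normally enlarge up to 5 years and then shrink, and these children are aged 2 to 6. A value frozen when the adenoid is at its largest would favour the arm with less surgery.

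Finally, this is a secondary comparison that was never powered. Under the trial's own hypothesis the bias runs against OM-85, so it would not produce a false efficacy claim. Both statements are right and limit the weight of the point.

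**Conclusion.** The concern holds in conditional form. The plan expects surgery in this disease, lists surgery need as an endpoint, schedules adenoid measurement in every child for 12 months and gives no rule for values after adenoidectomy. Used as measured, those values favour the arm with more surgery; exclusion reduces the bias without removing it.

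The size cannot be taken from the documents. Under the assumptions above, a true benefit of 10 points would appear as anything from about 9 points to about zero or slightly below, depending mainly on how far surgery rates differ. For scale, the smallest significant difference with 27 per arm and SD 20 is 10.9 points, so the larger shifts are comparable with what the trial could detect. With equal surgery rates and no true effect there is no net mean bias.

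It should not be read as a finding that the plan prescribes the use of post-operative values, or that operations during follow-up are certain. It concerns a secondary endpoint, although adenoid size is in the study title. The primary endpoint and its sample size are untouched.

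**What to change.** In the SAP:

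- State that adenoid measurements after adenoidectomy are not used as measured.
- For the 12-month comparison, rank operated children worst in the Mann-Whitney test the plan already names.
- Show two sensitivity analyses: the last pre-operative value carried forward, and exclusion of operated children.
- Define surgery need, separating surgery indicated from surgery performed, and report both by arm.

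In Table 5, add whether an operation has taken place and its date.

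The cost is one SAP paragraph, one definition and two form fields. There is also a statistical cost. The worst-rank test combines size and surgery, so it must be described that way and shown beside the separate surgery results. It can also lose some power when surgery rates are equal: in the run above, 31% at 10% surgery in each arm against 42% with no surgery. Neither sensitivity analysis is unbiased; they show how far the result depends on the handling of operated children.
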